1. SYNOPSIS

Name of Sponsor/Company:

La Jolla Pharmaceutical Company (La Jolla)

Name of Investigational Product:

LJPC-501 (angiotensin II)

Name of Active Ingredient:

angiotensin II

Title of study:

An Open-label, Multi-Center Study of LJPC-501 in Pediatric Patients Who Remain Hypotensive Despite Receiving Fluid Therapy and Vasopressor Therapy

Number of study center(s): Approximately 10

Objectives:

Primary:

• To evaluate the effect of LJPC-501 infusion on mean arterial pressure (MAP) or reduction in sum norepinephrine-equivalent dose (NED), at Hour 2 after the start of LJPC-501, in pediatric patients who remain hypotensive despite receiving fluid therapy and vasopressor therapy.

Secondary:

- To establish the safety and tolerability of LJPC-501 in pediatric patients
- To evaluate the change in MAP over 24 hours after the start of LJPC-501
- To evaluate the change in serum lactate concentrations
- To evaluate change in Pediatric Logistic Organ Dysfunction (PELOD) scores

Methodology:

Screening

During Screening, there will be a titration period of standard of care (SOC) vasopressors (for a minimum of 2 hours to a maximum of 48 hours) to achieve an age-, size-, and disease-appropriate MAP (Appendix A, Dellinger 2013) at the discretion of the Investigator. Baseline MAP is defined as the average of 3 recorded MAP values documented within 15 minutes prior to initiation of LJPC-501 (ie, approximately -15 minutes, -5 minutes, and 0 minutes or just prior to initiation of LJPC-501 administration).

Administration and Assessments

Following informed consent/assent per institutional requirements, as age appropriate, and confirmation of eligibility, patients will begin LJPC-501 treatment at a dose rate of 5 ng/kg/min. To assess multiple possible improved outcomes for pediatric patients, the primary endpoint is a composite of improvement in MAP or reduction in sum NE equivalent dosing. The goal at Hour 2 of LJPC-501 administration is to increase the Baseline MAP by 25% or to decrease the sum NED by 25% at the 2-hour time point.

LJPC-501 dose rate will be titrated during the first 2 hours according to protocol guidelines and the Investigator's discretion, to achieve a MAP above baseline, but less than 90 mmHg. During the first 2 hours and throughout treatment, the LJPC-501 dose rate may be increased to a maximum rate of 40 ng/kg/min, and decreased to a minimum of 1.25 ng/kg/min. If MAP exceeds 90 mmHg, SOC vasopressors should be down-titrated first, then LJPC-501 should be down-titrated if MAP remains \geq 90 mmHg. Any decision to increase the dose rate above 40 ng/kg/min must be made in consultation with Sponsor. With Sponsor approval, the dose rate may be increased to a maximum of 80 ng/kg/min. Unless adjustment is required for safety reasons, SOC vasopressor dosing may be decreased, but not increased, the first 2 hours of LJPC-501 treatment (ie, up to the Hour 2 time point). MAP should not be allowed to decrease below baseline.

During LJPC-501 dosing, MAP should be assessed once every 5 minutes during the first 15 minutes of treatment, then once every 15 minutes up to the Hour 2 time point and at least once hourly thereafter through the duration of LJPC-501 administration (a minimum 24 hours). Additionally, MAP should be assessed once prior to every dose rate titration.

Treatment will continue to Hour 24, with the goal of maintaining age-, size-, and disease-appropriate MAP, and sparing the use of SOC vasopressors. At Hour 24, LJPC-501 treatment may be stopped or continued up to Day 7 (168 hours) at the Investigator's discretion, and consultation with Sponsor. To stop treatment, LJPC-501 will be down-titrated in steps to avoid transient hypotension. If the Investigator determines that it is necessary to discontinue LJPC-501 prior to Hour 24, the Sponsor should be notified.

If LJPC-501 treatment has been stopped for 3 hours or less (after the Hour 24 assessments), the Investigator may reinitiate treatment after consultation with Sponsor; if treatment has been stopped for more than 3 hours it may not be reinitiated. All patients will be followed for a minimum of 7 days, or for 72 hours (3 days) \pm 6 hours following discontinuation of LJPC-501, whichever is later, before the end of study (EOS) assessments are collected.

All components of the PELOD, PRISM, and PIM2 scores will be collected during Screening (no more than 6 hours prior to the initiation of LJPC-501 dosing) and at Hour 24. If possible, blood samples to determine the levels of endogenous angiotensin II and its precursor, angiotensin I, will be obtained at Screening prior to LJPC-501 administration.

Assessment of Safety

Safety will be addressed by assessing adverse events (AEs), blood pressure (BP), heart rate (HR), and routine clinical safety laboratory testing including blood chemistry, hematology, and urine output. A follow-up phone call or chart review will occur at approximately 28 days following initiation of LJPC-501 for safety.

This study will be overseen by an independent external Data Safety Monitoring Board (DSMB).

Number of patients (planned): 10 to 30

Diagnosis and main criteria for inclusion:

- 1. Pediatric patients 2-17 years of age and weighing ≥ 10 kg.
- 2. Patients requiring a sum norepinephrine-equivalent dose of $> 0.1 \mu g/kg/min$ (see Appendix B for conversion) for a minimum of 2 hours and a maximum of 48 hours prior to initiation of LJPC-501 dosing.
- 3. Patients must have a clinical diagnosis of distributive shock in the opinion of the treating team and the Investigator.
- 4. Patients are required to have central venous access, which is expected to remain present for the duration of LJPC-501 treatment.
- 5. Patients are required to have an indwelling arterial line, which is expected to remain present for at least the first 24 hours of LJPC-501 treatment.
- 6. Patients must have received at least 40 mL/kg of crystalloid or colloid equivalent over the initial 24-hour resuscitation period, and are adequately volume resuscitated in the opinion of the Investigator.
- 7. Patients should receive venous thromboembolism (VTE) prophylaxis per institutional guidelines, if indicated, before beginning treatment with LJPC-501.
- 8. Parent or legal guardian is willing and able to provide informed consent and assist the patient in complying with all protocol requirements.

Exclusion Criteria:

- 1. Patients who are < 2 years of age or ≥ 18 years of age.
- 2. Patients who weigh < 10 kg.
- 3. Patients with a standing Do Not Resuscitate order.
- 4. Patients diagnosed with acute occlusive coronary syndrome requiring pending intervention.
- 5. Patients on veno-arterial (VA) extracorporeal membrane oxygenation (ECMO).
- 6. Patients who have been on veno-venous (VV) ECMO for less than 6 hours.
- 7. Patients with a clinical suspicion of cardiogenic shock
- 8. Patients who have a history of asthma or are currently experiencing bronchospasm requiring the use of inhaled bronchodilators and who are not mechanically ventilated.
- 9. Patients with acute mesenteric ischemia or a history of mesenteric ischemia.
- Patients with active bleeding AND an anticipated need of multiple transfusions (within 48 hours of Screening).
- 11. Patients with active bleeding AND hemoglobin < 7 g/dL or any other condition that would contraindicate serial blood sampling.
- 12. Patients requiring more than 5 mg/kg daily of hydrocortisone or equivalent glucocorticoid medication as a standing dose.
- 13. Patients with an expected lifespan of < 12 hours or withdrawal of life support within 24 hours of Screening.
- 14. Patients with a known allergy to mannitol.
- 15. Patients who are currently receiving an investigational drug (active or placebo) as part of another clinical trial.

16. Patients of childbearing potential who are known to be pregnant at the time of Screening.

Investigational product, dosage and mode of administration:

LJPC-501 for intravenous (IV) infusion: 2.5 mg per mL

Patients will begin LJPC-501 treatment by IV infusion at a dose rate of 5 ng/kg/min. The dose rate may escalate up to 40 ng/kg/min in order to achieve and maintain an age-, size-, and disease-appropriate MAP greater than baseline (above baseline, but less than 90 mmHg, per Investigator discretion). Throughout treatment, LJPC-501 dose rate may be increased to a maximum rate of 40 ng/kg/min, and decreased to a minimum of 1.25 ng/kg/min. Any decision to increase the dose rate above 40 ng/kg/min must be made in consultation with Sponsor. With Sponsor approval, the dose rate may be increased to a maximum of 80 ng/kg/min. Dose administration for more than 24 hours, and for up to 7 days, is permitted with Sponsor consultation.

Duration of treatment:

The target minimum duration of treatment is 24 hours. Continued administration of LJPC-501 for up to 7 days is permitted after consultation with the Sponsor.

Criteria for evaluation: Efficacy:

Primary composite endpoint:

• Proportion of patients with an increase of 25% over Baseline MAP (without an increase in sum NED from baseline) at 2 hours after the initiation of LJPC-501 OR a 25% reduction in sum NED (without a decrease in MAP from baseline) at 2 hours after the initiation of LJPC-501

Secondary endpoints:

- Adverse events, BP, HR, and routine clinical safety laboratory testing including blood chemistry, hematology, and urine output
- Change in MAP from baseline to 24 hours
- Change in concentration of serum lactate from baseline to 2 hours and to 24 hours
- Change in PELOD score from Screening to 24 hours

Exploratory endpoints:

- Change in tissue oxygenation from baseline to 2 hours and to 24 hours
- Change in HR from baseline to 2 hours
- Change in sum NED from baseline to 24 hours
- 28-day all-cause mortality
- Number of ventilator days
- Number of days on a vasopressor
 - Change in PRISM and PIM2 scores from Screening to 24 hours

Statistical methods:

٠

Data will be summarized and reported in a descriptive fashion. All patients who receive any amount of LJPC-501 will be included in the safety evaluation.

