5.5. Exploratory Endpoints

- Change in tissue oxygenation from baseline to 2 hours and to 24 hours
- Change in HR from baseline to 2 hours
- Change in sum NED from baseline to 24 hours
- 28-day all-cause mortality
- Number of ventilator days
- Number of days on a vasopressor
- Change in PRISM and PIM2 scores from Screening to 24 hours

La Jolla Pharmaceutical Company - Confidential 19 March 2018 (Version 2.0)

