All components of the PELOD, PRISM, and PIM2 scores will be collected during Screening (no more than 6 hours prior to the initiation of LJPC-501 dosing) and at Hour 24. If possible, blood samples to determine the levels of endogenous angiotensin II and its precursor, angiotensin I, will be obtained at Screening prior to LJPC-501 administration. Safety will be addressed by assessing AEs, BP, HR, and routine clinical safety laboratory testing including blood chemistry, hematology, and urine output. A follow-up phone call and/or chart review will occur at approximately 28 days following initiation of LJPC-501 for safety assessments.

This study will be overseen by an independent external Data Safety Monitoring Board (DSMB).

Abbreviations: EOS=end of study; SOC=standard of care

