- ¹⁷ Blood for clinical chemistry and hematology testing will be collected at Screening (within 6 hours prior to LJPC-501 administration), and at Hour 24 (Section 11.1.8).
- ¹⁸ If total blood collection volume limits (per institutional guidelines) allow, blood samples will be collected for angiotensin I/II levels.
- ¹⁹ See Section 6.2 and Section 6.6 for study periods and dose adjustment guidelines. (X) indicates time periods during which dose administration is optional.
- ²⁰ All parameters of the PELOD/PRISM/PIM2 scores should be performed at Screening and at Hour 24. The Screening PELOD/PRISM/PIM2 scores must be determined with data obtained no more than 6 hours prior to initiation of LJPC-501 dosing. See Appendix C, Appendix D, and Appendix E.
- ²¹ Record all concomitant medications (including vasopressors) and any procedures performed through Day 28. In addition, record all vasopressors administered up to 2 days prior to beginning LJPC-501 administration. Total daily dose for each vasopressor administered through Day 28 may be recorded after completion of LJPC-501 administration.
- ²² Safety will be evaluated at every time point. On Day 28, a phone call follow-up to the patient's parent(s) or legal guardian(s), the patient's primary care physician, and/or a chart review will be conducted to determine if reportable safety events occurred between EOS and Day 28.

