8.5.11. Day 28 Follow-up

- Record concomitant medications and procedures administered between EOS and Day 28
- Assess SAEs via phone call to the patient's parent(s) or legal guardian(s), the patient's primary care physician, and/or a chart review

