11.2.1.2. Serious Adverse Event (SAE)

A serious adverse event (experience or reaction) is an AE that results in one or more of the following:

- Results in death An adverse event that caused or contributed to a fatal outcome
- Is life-threatening Refers to an event/reaction in which the patient was at risk of death at the time of the event/reaction; it does not refer to an event/reaction which hypothetically might have caused death if it were more severe.
- Requires inpatient hospitalization or results in prolongation of existing hospitalization.
- Results in persistent or significant disability/incapacity
- Results in a congenital abnormality or birth defect
- Important medical events when based upon appropriate medical judgment, may jeopardize the patient or subject and may require medical or surgical intervention to prevent one of the outcomes listed in this definition.

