11.2.4.2. Reporting of Serious Adverse Events

In agreeing to the provisions of this protocol, the Investigator accepts all legal responsibilities for immediately reporting of SAEs to La Jolla. Immediate reporting implies within 24 hours of becoming aware of the occurrence of a SAE.

All SAEs that occur from initiation of study drug treatment, during treatment, and through the Day 28 follow-up, regardless of the causal relationship to the investigational product, must be reported to La Jolla by following the instructions provided in this Section. Redacted medical record source documentation will be requested for all SAEs and emergency room visits.

The method for reporting a SAE is by completing and sending the Serious Adverse Event Report Form and completing the AE CRF. The Serious Adverse Event Report Form and if applicable, a copy of redacted source documents (such as hospital discharge summary, medical records, etc.) related to the SAE will be sent as:

- e-mail to: [contact]; or
- fax to: [contact]

The Investigator will assess whether the event is causally related to the investigational product. La Jolla will also assess whether the event is causally related to the investigational product, in addition to assessing the overall safety profile of the investigational product. La Jolla will notify the appropriate regulatory authorities in accordance with country regulations. It is the Investigator's responsibility to notify the IRB or independent ethics committee (IEC) of all SAEs that occur at his or her site, according to local requirements. Investigators will be informed about SAEs according to applicable local regulations. Each site is responsible for notifying its IRB/IEC of these additional SAEs, per local policy.

Following the initial report, any additional information obtained by the Investigator about the SAE must be reported promptly to La Jolla in the same manner as described above for the initial SAE report.

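### Chart review alone is accepted as the Day 28 follow-up even for a child who has left the treating hospital, so late SAEs and deaths elsewhere can be missed

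*Protocol*

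**What the plan says.** Four places in the protocol describe the Day 28 contact.

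- Synopsis, Assessment of Safety: "A follow-up phone call or chart review will occur at approximately 28 days following initiation of LJPC-501 for safety".
- Section 6.2: "A follow-up phone call and/or chart review will occur at approximately 28 days following initiation of LJPC-501 for safety assessments".
- Table 4, footnote 22: after naming a call to the parents or guardians and the primary care physician, joined by and/or, it says that "a chart review will be conducted to determine if reportable safety events occurred between EOS and Day 28".
- Section 8.5.11: "Assess SAEs via phone call to the patient's parent(s) or legal guardian(s), the patient's primary care physician, and/or a chart review".

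Three other provisions depend on what this contact finds.

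- Section 11.2.4.2 requires reporting of "All SAEs that occur from initiation of study drug treatment, during treatment, and through the Day 28 follow-up", whatever the causal relationship.
- Section 11.2.1.2 counts as serious an event that "Requires inpatient hospitalization or results in prolongation of existing hospitalization".
- Section 5.5 lists "28-day all-cause mortality" as an exploratory endpoint.

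The last required direct assessment is EOS. Table 4 footnote 2 places it between Day 7 and Day 10, and on Day 7 for a child treated for the target minimum of 24 hours.

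**The concern.** A chart shows what happened at the hospital that keeps it. For a child still in the treating hospital on Day 28, it is a sound source for death and for SAEs. For a child who has gone home or been transferred, it need not show a death, readmission or thrombotic event handled elsewhere. The protocol accepts the same method in both situations.

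Any resulting error runs one way, towards fewer SAEs and fewer deaths. The study has one arm and is reported descriptively (Sections 6.3 and 12), so the absolute rates are the result and there is no control group in which the same undercount would occur. Safety and tolerability are a secondary objective (Section 5.3). Section 4.6 reports more thromboembolic events with the drug than with placebo in adults (12.9% versus 5.1%) and calls the thrombosis risk in children unknown, so late serious events are of interest. Because the choice of method is left open, a call may be made for some children and only a chart opened for others.

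**Working it through.** The point rests on wording. The protocol gives no expected 28-day mortality or loss to follow-up for this trial, so there is no planned figure to reproduce.

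**Step 1. Does any of the four descriptions limit chart review?** The synopsis joins the two methods by *or*; the other three use *and/or*. None makes the method depend on whether the child is an inpatient, discharged or transferred. None says whose chart is meant, requires confirmation of vital status, or says what to record when the chart has no entry after discharge.

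**Step 2. How much time rests on this contact?** Table 4 schedules nothing between EOS and Day 28.

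- EOS on Day 10: 28 − 10 = 18 days
- EOS on Day 7: 28 − 7 = 21 days

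About 18 to 21 of the 28 days therefore depend on the Day 28 contact for new events.

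**Step 3. Do other duties supply the information?**

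| Duty | Where | What it leaves open |
|---|---|---|
| SAE reporting: "Immediate reporting implies within 24 hours of becoming aware of the occurrence of a SAE" | Section 11.2.4.2 | Starts only once the site knows of the event |
| Medications and procedures recorded through Day 28 | Sections 8.2, 8.5.11 and 11.1.1; Table 4 footnote 21 | Needs information from after discharge, but the method stays open |
| Missing data to be explained | Section 14 | Applies if the site sees that something is missing |
| Ongoing AEs that are related or of other clinical significance followed further | Section 11.2.5 | Covers events already known at the final visit, not new ones |

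Each reduces the gap. None guarantees that a new event elsewhere reaches the site.

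**Step 4. Scale.** Section 6.4 plans 10 to 30 patients. One missed death lowers the observed 28-day mortality by 1/N:

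- N = 30: 1/30 = 3.3 percentage points
- N = 20: 1/20 = 5.0 percentage points
- N = 10: 1/10 = 10.0 percentage points

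As an illustration, Section 4.2 cites mortality of 8.9% to 14.4% in pediatric severe sepsis, while noting that outcomes in the trial's own population are not specifically described. If that range applied, expected deaths would be:

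- N = 10: 10 × 0.089 = 0.9 to 10 × 0.144 = 1.4
- N = 30: 30 × 0.089 = 2.7 to 30 × 0.144 = 4.3

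One missed death would be a large part of such totals. These figures show what one miss would do, not how likely it is. The likelihood depends on the share of children who leave the site before Day 28, which the protocol does not give.

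**The case against.** A reader might infer that a site can open its own chart, find nothing after discharge, enter no event and be fully compliant. The protocol does not say so, and several provisions weigh against it. Footnote 22 defines the contact by its purpose, which is to establish whether reportable events occurred after EOS; a chart that ends at discharge does not establish that. Medications and procedures through Day 28 cannot come from such a chart. Section 14 makes the investigator responsible for completeness and asks for missing data to be explained. Section 11.2.4.2 requests records for emergency room visits as well as SAEs. This part of the objection stands: a silent entry of no event would fit badly with these duties.

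Three further inferences also go too far.

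- *Ascertainment differs by site.* No section assigns a method by site. It can differ by site or by patient.
- *Only the site's own chart is meant.* The text does not restrict whose chart is reviewed, and it names the parent or guardian and the primary care physician first.
- *Nothing else follows the child after EOS.* Section 11.2.5 continues follow-up of certain known events, so the exposure concerns new ones.

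It is also fair that the consequence is limited: 28-day mortality is exploratory, and non-serious AEs stop at EOS by design (Section 11.2.4.1).

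What remains is that the duties cited against the concern depend largely on the site learning of an event, and the one scheduled contact that could tell it may be replaced by a chart review for any child.

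**Conclusion.** The point holds as a modest, inexpensive improvement to a data-collection rule. For children discharged or transferred before Day 28, chart review alone can miss new SAEs and deaths after EOS, and any such misses bias the SAE counts and the exploratory 28-day mortality downward. One missed death is worth 3.3 to 10 percentage points for N = 30 to 10. The expected bias cannot be estimated, because neither the discharge share nor the use of chart review alone is known.

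The conclusion assumes that at least some children leave the treating hospital before Day 28 and that the chart reviewed does not always include records from elsewhere. The primary endpoint and the success rule in Section 12 use Hour 2 data only and are not affected. A statistical analysis plan could not repair the gap, since it cannot recover events that were never collected.

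**What to change.** Align the synopsis, Section 6.2, Table 4 footnote 22 and Section 8.5.11 on one rule:

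- Accept chart review alone only if the child is still an inpatient at the site, or has died there, by Day 28.
- For any other child, require contact with the parent or guardian, the primary care physician or the receiving hospital, to confirm vital status and SAEs since EOS.
- If contact fails, treat vital and SAE status as unknown, not as event-free.

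The first two contacts are already listed in the protocol; only the receiving hospital is new. Noting which source was used would help interpretation, but that is secondary and can be left to the case report form instructions.

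The cost is a wording change in four places and about one phone call for each discharged or transferred child at sites that would otherwise have used only the chart. Treatment is not changed.
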